13.5. Analysis of Primary Endpoints

Time to local failure on a per metastasis basis will be performed using the Kaplan-Meier curves, the log-rank test, and Cox regression for clustered data. Inpatient correlations will be accounted for using a sandwich estimator.

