13. STATISTICAL CONSIDERATIONS

13.1. Study Design/Endpoints

The primary endpoint of this study is local control on a per metastasis level. This study seeks to evaluate, in a signal-finding randomized phase II study, whether brain-directed stereotactic radiation in the presence of AGuIX nanoparticles demonstrates a signal towards improved local control relative to brain-directed stereotactic radiation alone. The study will have one phase. We will capitalize on the fact that many patients will harbor more than one intracranial tumor. Accordingly, even after accounting for intra-patient correlations, we can conduct a randomized trial with a smaller sample size than would typically be required. The study seeks to accrue 474 brain metastases from approximately 134 patients over a period of approximately 2.8 years. We plan to accrue approximately 47-48 patients per year. All patients will be followed for at least 12 months; however, the primary analysis point will be mature 6 months post the end of recruitment (in order to maintain statistical power).

We hypothesize that brain metastases will display a signal toward improved local control when managed with brain-directed stereotactic radiation and concurrent AGuIX nanoparticles as opposed to stereotactic radiation alone. In total 474 brain metastases from 134 patients would provide 90% power to detect a HR of 0.60 with radiation and AGuIX nanoparticles using a baseline local recurrence rate of 27.5% at one year (among historical controls managed with radiation alone at Brigham and Women's Hospital/Dana-Farber Cancer Institute), a one-sided type I error of 0.10, an accrual period of 2.8 years, a minimum follow up period of 6 months and 20% inflation for the competing risk of systemic death, and 33% inflation for intra-patient correlation among metastases. A stratified, correlated log rank test will be the primary method of analysis. Given this design, a final one-sided p value <0.10 in this hypothesis-generating study will suggest that a phase III randomized trial comparing brain-directed stereotactic radiation with or without AGuIX nanoparticles for patients with brain metastases is warranted.

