13.3. Stratification Factors

As noted above patients will be stratified into the following strata:

- Melanoma with intracranial growth consistent with tumor progression despite immunotherapy
- Gastrointestinal primary
- HER2 positive breast cancer
- Cystic metastases
- Metastases ≥ 2 cm in maximal unidimensional size
- Locally recurrent metastases after prior stereotactic radiation
- Locally recurrent metastases after prior whole brain radiation

Patients with metastases from melanoma, GI primaries, or HER2+ breast cancer, as well as those with cystic metastases or metastases ≥ 2 cm in maximal unidimensional size, who have local recurrences after prior brain-directed radiation can only be treated in the strata permitting prior radiation (last two strata above).

We will mandate that each stratum contain at least 12 patients by the end of the study in order to ensure a reasonable number of patients per stratum, with the exception of the locally recurrent metastases after prior stereotactic radiation stratum, which may be closed early if at least 12 patients have been accrued to the other strata. The treatment naïve metastases ≥ 2 cm in maximal unidimensional size stratum will target 44 patients as this stratum represents an important and prevalent brain metastasis population. No other stratum will be permitted to accrue more than 22 patients. Accrual to individual strata will be monitored as the study progresses.

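### With seven mostly small strata, the primary test with an uncorrected sandwich variance runs at about 0.11-0.12 one-sided, not the stated 0.10

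*Protocol*

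**What the plan says.** Protocol section 13.1 names the primary test: "A stratified, correlated log rank test will be the primary method of analysis". It sets the error rate with "a one-sided type I error of 0.10, an accrual period of 2.8 years, a minimum follow up period of 6 months" and ties the conclusion to it: "a final one-sided p value <0.10 in this hypothesis-generating study will suggest that a phase III randomized trial" is warranted. The size claim is "474 brain metastases from 134 patients would provide 90% power to detect a HR of 0.60".

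Section 13.5 lists Kaplan-Meier curves, the log-rank test and Cox regression for clustered data, with within-patient correlation "accounted for using a sandwich estimator". It does not repeat that the test is stratified; that comes from section 13.1, which also plans a stratified, clustered log-rank test at the interim look.

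Section 13.3 lists seven strata. The stratum of treatment-naive metastases of 2 cm or more targets 44 patients. The others are to reach at least 12 (the post-stereotactic-radiation stratum may close early), and "No other stratum will be permitted to accrue more than 22 patients". The protocol states no small-sample correction, t reference or permutation reference.

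**The concern.** Planning around 474 metastases makes the sample look large, but a patient-clustered sandwich variance learns from patients, and in a stratified test from patients within each stratum. Lesion residuals are taken around risk-set means estimated in that same stratum. With 6-11 patients per arm in most strata, those residuals are systematically too small, and so is the variance. The test statistic is then too large under the null.

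The p < 0.10 rule is the protocol's criterion for suggesting a phase III trial. If the test runs above 0.10, somewhat more ineffective treatments would pass than the design says.

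**Working it through.** **1. The plan's own figure.** Inputs from section 13.1: HR 0.60, one-sided 0.10, 90% power, "using a baseline local recurrence rate of 27.5% at one year", 2.8 years of accrual, 6 months of minimum follow-up, and "20% inflation for the competing risk of systemic death, and 33% inflation for intra-patient correlation among metastases".

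- Events (Freedman): (1.2816 + 1.2816)² × [(1 + 0.6)/(1 − 0.6)]² = 6.57 × 16 = 105.1.
- Control hazard: −ln(1 − 0.275) = 0.3216 per year; experimental 0.6 × 0.3216 = 0.1930.
- Event probability, uniform accrual: 1 − [exp(−0.5λ) − exp(−3.3λ)]/(2.8λ) = 0.439 and 0.298, mean 0.3686.
- Metastases: 105.1/0.3686/0.80 × 1.33 = 474.1.

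The 474 reproduces. This calculation assumes a test that holds one-sided 0.10.

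**2. Stratum sizes.** 134 − 44 = 90 patients in six strata, average 90/6 = 15, or 7-8 per arm. The limits of 12 and 22 mean 6 to 11 per arm.

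**3. Size to expect.** As a heuristic, suppose each stratum loses two degrees of freedom, one per arm. The sandwich then captures about (134 − 2 × 7)/134 = 120/134 = 0.896 of the variance. The level becomes 1 − Φ(1.2816 × √0.896) = 1 − Φ(1.213) = 0.113.

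**4. Simulation under HR 1.** 134 patients; 1:1 allocation within strata; 1-10 metastases per patient (mean 3.54) unless noted; 27.5% one-year recurrence; gamma frailty shared within patient; death as censoring at 0.45 per year; single test at 1.2816. There were 12,000 trials per row (Monte Carlo SE about 0.003). The base row has strata of 44 and 6 × 15, blocks of 4 and frailty variance 0.25. Its design effect is 1.33, matching the protocol's 33% inflation. Each cell gives the tail favouring AGuIX / the other tail.

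| Setting | Robust score | Robust Wald | Permutation variance | Score sandwich/true variance |
|---|---|---|---|---|
| Base | 0.117 / 0.119 | 0.119 / 0.122 | 0.102 / 0.102 | 0.877 |
| Frailty 0 | 0.117 / 0.110 | 0.119 / 0.110 | 0.105 / 0.095 | 0.907 |
| Frailty 1 | 0.112 / 0.122 | 0.115 / 0.125 | 0.095 / 0.104 | 0.878 |
| Frailty 2 | 0.115 / 0.120 | 0.118 / 0.124 | 0.097 / 0.105 | 0.876 |
| Strata 44, 4 × 12, 20, 22 | 0.110 / 0.121 | 0.114 / 0.124 | 0.095 / 0.105 | 0.880 |
| Simple randomization | 0.121 / 0.117 | 0.125 / 0.120 | 0.105 / 0.100 | 0.866 |
| 3-4 lesions for every patient | 0.111 / 0.112 | 0.113 / 0.113 | 0.099 / 0.101 | 0.914 |
| Unequal stratum hazards | 0.119 / 0.116 | 0.121 / 0.120 | 0.102 / 0.100 | 0.884 |

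The variance ratios explain most of this: 1 − Φ(1.2816 × √0.877) = 0.115 and 1 − Φ(1.2816 × √0.914) = 0.110.

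In smaller runs (2,000 trials, SE about 0.007), death hazards of 0 to 1.0 per year gave 0.107-0.121 for the score test. The same sandwich without strata gave 0.092-0.103, so the excess comes from combining the sandwich with small strata. Separately written simulations (4,000-6,000 trials per setting) gave 0.109-0.119 with near-equal counts and 0.113-0.129 with skewed counts in one set, and 0.110-0.124 over both kinds of counts in another. The permutation variance gave 0.096-0.113 across the separate sets.

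**5. Corrections.** Multiplying each stratum's contribution by n/(n−1) left 0.104-0.116. Using n/(n−2) gave 0.096-0.100 with near-equal counts and 0.108-0.109 with skewed counts.

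**The case against.** The protocol says only that a sandwich estimator is used. It does not say uncorrected, and it fixes no reference distribution. A reader might infer that it commits to a defective variant, or that every sandwich-based test fails here. Neither follows: the n/(n−2) form is still a sandwich and comes close to the level, and an analysis plan that is not shown could specify it. Joining the stratified test of section 13.1 to the variance of section 13.5 is also an inference, though the natural one. What remains is that the standard form of the named test, applied to the stated strata, misses the stated level.

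A reader might also take a higher figure. One less common form of clustered log-rank variance, with arm-specific hazards, gave 0.126-0.147, but the protocol does not name it, so that range should not be attributed to the plan.

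The figures are not the error rate of the full procedure, which has an O'Brien-Fleming look at half information. A rough calculation with Lan-DeMets boundaries (2.054 and 1.316), the same variance ratio of 0.87-0.91 at both looks and no further simulation gives about 0.112-0.118 overall. The interim look therefore does not obviously remove the excess, but this is an approximation.

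Finally, section 13.1 calls the trial hypothesis-generating and says a low p-value will suggest a phase III trial. It is not an automatic trigger, and one or two points on a lenient 0.10 is a small matter. That stands, and it limits the weight of the point.

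**Conclusion.** The point holds in a limited form. With 134 patients in seven strata, the standard sandwich without a small-sample correction understates the variance by roughly 10%. The one-sided level at a single final look is then about 0.11-0.12, reaching about 0.125-0.13 in some settings. Skewed lesion counts are not needed to produce it.

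The result rests on assumed lesion-count distributions, frailty variance 0-2, death hazard 0-1.0 per year and exact stratum sizes. The direction was the same in every stratified 12,000-trial setting. It does not call the 474-metastasis calculation into question, and it does not invalidate the design. It is a modest, easily removed gap between the stated and the delivered error rate.

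**What to change.** Take the primary p-value from a permutation test, or permutation variance, of the same stratified clustered log-rank score, permuting arm by patient within stratum. Use the same reference at the interim look. Keep the sandwich-based Cox model for the hazard ratio and its interval.

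If a corrected sandwich is preferred, name the form and show by simulation that it holds 0.10 with the realised strata and lesion counts. The n/(n−1) correction per stratum is not enough; n/(n−2) is closer, at about 0.10-0.11.

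The cost is a little analysis code, with no change to sample size, conduct or follow-up. In three simulated settings at HR 0.60, rejection rates for sandwich against permutation were 0.813 against 0.793, 0.783 against 0.754, and 0.739 against 0.705, losses of 2.0, 2.9 and 3.4 points. Over all checks the loss was about 1-3.5 points of nominal power, largely the removed excess in the error rate. Those rates depend on assumed frailty and death and serve only for the comparison, not as a test of the 90% power claim.

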13.6. Analysis of Secondary Endpoints

Secondary endpoint will be analyzed as follows

1. Overall survival (i.e. all cause mortality) Kaplan-Meier curves, log-rank test, Cox regression)
2. Death due to neurologic disease progression (defined as death due to progressive brain metastases on imaging associated with progressive neurologic symptomatology in the setting of systemic disease that has not progressed to a life-threatening nature; cumulative incidence curves, Gray's test, Fine and Gray's regression)
3. Performance status, assessed longitudinally (longitudinal regression)
4. Ability to complete activities of daily living, assessed longitudinally (longitudinal regression)
5. Incidence and time to detection of new brain metastases (Kaplan-Meier curves, log-rank test, Cox regression)
6. Incidence and time to development of radiation necrosis (Kaplan-Meier curves, log-rank test, Cox regression)
7. Incidence and time to development of leptomeningeal disease (Kaplan-Meier curves, log-rank test, Cox regression)
8. Incidence and time to progressive intracranial disease (Kaplan-Meier curves, log-rank test, Cox regression)
9. Incidence and time to salvage craniotomy (Kaplan-Meier curves, log-rank test, Cox regression)
10. Incidence and time to additional radiotherapeutic treatments after the initial course (stereotactic or whole brain radiation) (Kaplan-Meier curves, log-rank test, Cox regression)
11. Progression free survival (Kaplan-Meier curves, log-rank test, Cox regression)
12. Incidence and time to the development of seizures (Kaplan-Meier curves, log-rank test, Cox regression)
13. Neurocognition, assessed longitudinally (longitudinal regression)
14. Quality of life, assessed longitudinally (longitudinal regression)
15. Steroid use, assessed longitudinally (longitudinal regression)
16. Local recurrence at one year in metastases treated radiotherapeutically using RECIST (response evaluation criteria in solid tumors) criteria (Kaplan-Meier curves, log-rank test, Cox regression)

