11.1.6. Other outcomes

Overall Survival: Overall Survival (OS) is defined as the time from enrollment to death due to any cause, or censored at date last known alive.

Progression-Free Survival: Progression-Free Survival (PFS) is defined as the time from enrollment to the earlier of progression of radiated lesions or death due to any cause. Participants alive without disease progression in radiated lesions are censored at date of last disease evaluation.

Time to Progression: Time to Progression (TTP) is defined as the time from enrollment to progression of radiated lesions, or censoring at date of last disease evaluation for those without progression reported.

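### Kaplan-Meier is specified for local failure, radiation necrosis and the other incidence outcomes although death competes with them, so the reported absolute risks would be too high

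*Protocol*

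**What the plan says.** Section 13.5 sets the primary analysis: "Time to local failure on a per metastasis basis will be performed using the Kaplan-Meier curves, the log-rank test, and Cox regression for clustered data". Section 13.6 names a method for each secondary endpoint. Seven endpoints are labelled as incidence and time to an event (items 5-10 and 12), and all get Kaplan-Meier, log-rank and Cox. Necrosis (item 6) reads "Incidence and time to development of radiation necrosis (Kaplan-Meier curves, log-rank test, Cox regression", and salvage craniotomy (item 9) follows the same pattern: "Incidence and time to salvage craniotomy (Kaplan-Meier curves, log-rank test, Cox regression". Local recurrence at one year by RECIST (item 16) is treated the same way.

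Only neurologic death (item 2) gets a competing-risk analysis: "cumulative incidence curves, Gray's test, Fine and Gray's regression".

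The sample size paragraph in section 13.1 includes "20% inflation for the competing risk of systemic death". The definition of local recurrence in section 11.1.5 does not count death as an event. Section 11.1.6 defines time to progression without death as an event, with "censoring at date of last disease evaluation for those without progression reported". These methods are fixed in the protocol itself, so this is not a matter left to a separate analysis plan.

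**The concern.** Kaplan-Meier with deaths censored estimates the risk in a hypothetical setting where nobody dies first. Incidence is the share of patients, or of metastases, that actually have the event. The two separate as deaths accumulate.

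Deaths will not be few. Section 3.1 requires an estimated survival of only 3 months. Section 2.3 reports ten deaths in the earlier whole-brain trial of this agent, in a paragraph that refers to 15 patients evaluated. Sections 5.6 and 10 follow patients until death or censoring, so the gap can grow over a long period.

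What is at stake is the absolute risks that readers will set against each other. Section 2.1 calls necrosis the primary long-term adverse effect of stereotactic radiation. Weighing fewer local failures against added necrosis needs the proportions that actually occur. If survival differs between arms, the overstatement differs between arms too.

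**Working it through.** **1. The plan's own figure.** Inputs from section 13.1: HR 0.60, one-sided type I error 0.10, power 90%, control recurrence 27.5% at one year, accrual 2.8 years, minimum follow-up 0.5 year, inflation of 20% for death and 33% for intra-patient correlation. Allocation is about 67 patients per arm (section 13.2).

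- Freedman's formula gives 106 events.
- The control hazard is λ = -ln(1 - 0.275) = 0.3216 per year. With uniform accrual, the mean event probability is 0.4387 in the control arm and 0.2985 in the experimental arm, average 0.3686.
- 106 / 0.3686 = 287.6 metastases, and 287.6 / (1 - 0.20) × 1.33 = 478, against 474 stated.

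The stated size is reproduced to within 1%. This calculation reads 27.5% as a rate net of death and allows for death separately.

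**2. 1-KM against actual incidence.** Assume constant, independent hazards: λ for the event and μ for death, with μ = -ln(1 - one-year mortality).

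- 1-KM(t) = 1 - exp(-λt)
- Cumulative incidence: CIF(t) = λ/(λ+μ) × [1 - exp(-(λ+μ)t)]

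Example at 50% one-year mortality: μ = 0.693 and λ+μ = 1.015. CIF(1) = 0.3216/1.015 × (1 - 0.725 × 0.50) = 0.317 × 0.6375 = 0.202.

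The protocol gives no mortality rate, so the range below is an assumption. For local failure, with 27.5% at one year read as 1-KM:

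| One-year mortality (assumed) | 1-KM, 1 y | CIF, 1 y | 1-KM, 2 y | CIF, 2 y |
|---|---|---|---|---|
| 20% | 27.5% | 24.8% | 47.4% | 39.2% |
| 40% | 27.5% | 21.8% | 47.4% | 31.3% |
| 50% | 27.5% | 20.2% | 47.4% | 27.5% |
| 60% | 27.5% | 18.4% | 47.4% | 23.8% |

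For necrosis the protocol gives no rate. With an assumed one-year 1-KM of 15%:

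| One-year mortality (assumed) | 1-KM, 1 y | CIF, 1 y | 1-KM, 2 y | CIF, 2 y |
|---|---|---|---|---|
| 20% | 15.0% | 13.5% | 27.8% | 22.7% |
| 50% | 15.0% | 10.9% | 27.8% | 15.6% |
| 60% | 15.0% | 9.9% | 27.8% | 13.3% |

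**3. Which row is closest to the plan's allowance.** Without deaths, 474 metastases would give 474 × 0.3686 = 174.7 events. At 20% one-year mortality they give 142.4, a loss of 1 - 142.4/174.7 = 18.5%. That is close to the 20% allowance in section 13.1. In that row the gap for local failure is 2.7 points at one year and about 8 points at two years.

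**4. Unequal survival.** With the same necrosis hazard in both arms (1-KM 15% in each) and one-year mortality of 60% in one arm and 40% in the other, the actual one-year incidences are 9.9% and 11.8%. Kaplan-Meier would show no difference.

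**The case against.** The strongest reply is that no decision in the trial depends on these curves. Section 13.1 bases its conclusion on a one-sided p<0.10 from a stratified, correlated log-rank test, and the efficacy interim uses a log-rank test as well. Log-rank and Cox with deaths censored are valid comparisons of cause-specific hazards. The relative contrast also hardly moves. With HR 0.60 and 50% one-year mortality in both arms, the one-year ratio is 17.5/27.5 = 0.638 by 1-KM and 12.8/20.2 = 0.634 by cumulative incidence, although the absolute difference falls from 10.0 to 7.4 points. This stands. A reader might infer that the primary test or the sample size is unsound, and the documents do not support that.

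A reader might also infer that Kaplan-Meier would give a wrong control rate for a phase III trial. That does not follow. A log-rank design can properly use the net rate plus a separate allowance for death, as section 13.1 does. Entering a rate already reduced by death and then inflating for death would count death twice. For the same reason, naming death as a competing risk in the sample size does not by itself commit the plan to a cumulative incidence estimator. For a radiosensitiser, the net local-control rate is a defensible quantity in its own right.

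Two further limits stand. The protocol does not say for each item that death is censored; this is inferred from Kaplan-Meier on outcomes that do not list death, and item 8 (progressive intracranial disease) is not defined closely enough to be certain. Sections 11.1.5 and 11.1.7 also censor lesions given definitive local therapy after smaller growth and lesions in patients given salvage whole brain radiation. Making death a competing event does not remove that censoring.

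None of this rescues 1-KM as an estimate for outcomes the protocol itself labels as incidence.

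**Conclusion.** The concern holds for the reported absolute risks and no further. For local failure and items 5-10, 12 and 16, 1-KM with deaths censored will be at or above the actual incidence, and above it once events follow deaths. The direction does not depend on the mortality rate; the size does. Over assumed one-year mortality of 20% to 60%, local failure would be overstated by a factor of 1.1 to 1.5 at one year (27.5% against 24.8% to 18.4%) and 1.2 to 2.0 at two years (47.4% against 39.2% to 23.8%). The low end best matches the plan's own allowance, so the larger gaps should not be taken as established.

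These figures rest on constant, independent hazards and on reading 27.5% as 1-KM. The protocol does not say which it is. If 27.5% is already a cumulative incidence, the matching one-year 1-KM would be 30.5% to 40.4% over the same mortality range.

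The consequence is greatest for necrosis, where the absolute risk is set against the local-control benefit. The primary test, its p<0.10 criterion and the 474 metastases are unaffected.

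**What to change.** - In section 13.6, items 5-10, 12 and 16, and for the absolute local-failure rates in section 13.5, report Aalen-Johansen cumulative incidence with death as a competing event.
- For per-metastasis outcomes, use variance that allows for clustering within patient (robust or bootstrap).
- Keep the log-rank and Cox comparisons, and label them as comparisons of cause-specific hazards.
- A Kaplan-Meier curve for local control may stay if it is labelled as the net, death-censored rate.
- Keep Kaplan-Meier for overall survival (item 1) and progression-free survival (item 11), where death is an event.

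No new data, patients or visits are needed, and the plan already names cumulative incidence for item 2. The cost is a little more than wording: item 2 is a patient-level outcome, so the clustered variance for per-metastasis curves has to be added, with some extra analysis work.

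### Section 13.6 item 16 analyses recurrence per metastasis with an ordinary log-rank test and Cox model, without the within-patient clustering adjustment that 13.5 gives the primary endpoint; separately, 13.5 should repeat the stratification named in 13.1

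*Protocol*

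**What the plan says.** Protocol 13.6 gives each secondary endpoint its methods in brackets. Item 16 reads "Local recurrence at one year in metastases treated radiotherapeutically using RECIST (response evaluation criteria in solid tumors) criteria (Kaplan-Meier curves, log-rank test, Cox regression". The methods named are the same three as for overall survival (item 1), which has one record per patient. Item 16 has no clustering term and no reference back to 13.5.

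Protocol 13.5, for time to local failure per metastasis, names Kaplan-Meier curves, "the log-rank test, and Cox regression for clustered data", and adds a sandwich estimator for correlation within patients. It does not mention strata.

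Protocol 13.1 states: "A stratified, correlated log rank test will be the primary method of analysis". The efficacy interim described there is also stratified and clustered. On size, "The study seeks to accrue 474 brain metastases from approximately 134 patients over a period of approximately 2.8 years". The assumptions behind that number include an allowance of 20% for systemic death and one of 33% for correlation between lesions of the same patient. Section 13.3 lists seven randomisation strata.

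**The concern.** Lesions in one patient share histology, systemic therapy, prior treatment and host factors, so their recurrence times are correlated. All lesions of a patient are also in the same arm. A log-rank test or Cox model that counts them as independent therefore understates the standard error of the treatment comparison. The protocol accepts this for the primary endpoint, in both the sample size and the analysis. Item 16 applies other response criteria to the same kind of data without that protection. Clusters can be large, since section 3.2.4 allows up to 10 targets, or up to 20 after whole brain radiation.

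If the analysis were run as named, the RECIST result would be reported with intervals that are too narrow and p-values that are too small, beside a correctly clustered primary result.

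A smaller matter concerns the primary endpoint itself. Section 13.1 calls the primary test stratified, and 13.5, the section on primary analysis, leaves that word out.

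**Working it through.** **Inputs (Protocol 13.1):** 474 metastases, 134 patients, hazard ratio 0.60, 90% power, one-sided 0.10, 27.5% control recurrence at one year, accrual 2.8 years, minimum follow-up 0.5 year, 20% inflation for systemic death, 33% for within-patient correlation.

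**Step 1. Reproduce the plan's figure, to confirm that 1.33 is a working input.**
- Events (Freedman): ((1+0.60)/(1−0.60))² × (1.2816+1.2816)² = 16 × 6.5695 = 105.1, rounded up to 106. Schoenfeld gives 101.
- Control hazard: −ln(1−0.275) = 0.3216 per year.
- Event probability with uniform accrual A = 2.8 and minimum follow-up F = 0.5: 1 − [exp(−λF) − exp(−λ(A+F))]/(λA). Control 0.439, experimental 0.298, mean 0.3686.
- Lesions before inflation: 106/0.3686 = 287.6.
- With /0.80 for systemic death and ×1.33 for clustering: 478. Without rounding the events up: 105.11/0.36856 × 1.33/0.80 = 474.

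The stated 474 is reproduced, so a design effect of 1.33 is what the plan uses. The protocol does not say how the 20% is applied; dividing by 0.80 is the reading that fits.

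**Step 2. Effect of ignoring clustering at that design effect (DE).**
- Mean lesions per patient: 474/134 = 3.54.
- Implied intra-patient correlation, assuming equal cluster sizes: (1.33−1)/(3.54−1) = 0.13.
- Standard error understated by √1.33 = 1.153. Interval width is 1/1.153 = 0.867 of what it should be, about 13% too narrow.
- Coverage of a nominal 95% interval: 2Φ(1.96/1.153) − 1 = 0.911.
- True level, one-sided 0.10: 1 − Φ(1.2816/1.153) = 0.133.
- True level, two-sided 0.05 (assumed level): 2[1 − Φ(1.96/1.153)] = 0.089.

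**Step 3. Range over an assumed correlation**, DE = 1 + (3.54−1) × ICC:

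| ICC | DE | two-sided 0.05 becomes | one-sided 0.10 becomes |
|---|---|---|---|
| 0.05 | 1.13 | 0.065 | 0.114 |
| 0.13 | 1.33 | 0.089 | 0.133 |
| 0.30 | 1.76 | 0.140 | 0.167 |

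**Step 4. Simulation under no effect**, to separate clustering from strata. Assumed: 134 patients in seven strata (44 and six of 15), 1:1 within stratum, mean about 3.5 lesions per patient capped at 10, gamma frailty per patient, median survival 12 months, 1,500 runs per setting. Rejection rates at two-sided 0.05:

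| Frailty variance | Unclustered, unstratified | Cluster-robust, unstratified |
|---|---|---|
| 0 | 0.055 | 0.055 |
| 0.5 | 0.100 | 0.053 |
| 1 | 0.132 | 0.047 |
| 2 | 0.169 | 0.054 |

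When recurrence was also made to differ between strata (frailty variance 1), the cluster-robust unstratified test rejected in 0.038 and 0.041 of runs. The excess error thus comes from the missing cluster adjustment. Leaving out the strata is neutral to slightly conservative. The cluster-robust stratified test ran at 0.057 to 0.071, slightly liberal in these small strata, so stratification is not what repairs the error either.

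**The case against.** **Item 16 names families of methods, not variance estimators.** Cox regression does not exclude a sandwich variance, and an analysis plan that is not shown may add one. This explains how the gap may have arisen, but 13.5 and 13.6 are adjacent and only 13.5 adds clustering. The methods for item 16 are stated, and run as stated they assume independence that the protocol itself rejects.

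**The unit might be the patient.** The target-lesion criteria in 11.1.4.1 use a sum of diameters per patient, and no text attaches 3.5 lesions per patient to item 16 specifically. The item nevertheless speaks of recurrence in metastases, and the per-lesion reading is the natural one.

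**Little hangs on it.** This stands. Item 16 enters neither the efficacy interim, nor the futility rule, nor the final criterion. A reader might see it as an independent check on the primary endpoint, but the protocol gives it no such role, and under 11.1.7 the study PI makes all final determinations of recurrence for it too.

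**Strata.** A reader might infer that 13.6 drops a required stratification, or that missing strata make p-values wrong. Neither holds: 13.1 asks for strata only in the primary analysis and its interim, and step 4 shows no inflation from omitting them. A reader might also infer that two rival primary p-values could be set against the 0.10 threshold. But 13.1 ties that threshold to the stratified, correlated test, and 13.5 is silent on strata rather than specifying an unstratified test. What remains is a missing word.

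**Conclusion.** The point holds for item 16. As written, a lesion-level endpoint gets an analysis for independent observations, with the loss of precision control calculated in step 2. Those figures rest on the protocol's own 33% and, for the two-sided level, on a significance level that the protocol does not state. The higher simulated rates of 0.100 to 0.169 depend on assumed frailty variances and lesion counts and should not be read as properties of this trial.

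The primary test keeps its clustering, so the trial's main conclusion is not affected. The difference between 13.1 and 13.5 over strata is a matter of consistency and efficiency, not of validity. This is a change that should be made to a secondary endpoint in a hypothesis-generating phase II trial.

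**What to change.** - **13.6, item 16:** replace the bracketed methods with Kaplan-Meier curves, the log-rank test for clustered data, and Cox regression with sandwich variance clustered on the patient, as in 13.5. Add one sentence applying the same to any other secondary outcome analysed per lesion. If one result per patient is intended for item 16, say so instead.
- **13.5:** add that the log-rank test and the Cox model are stratified by the randomisation strata, to match 13.1.
- **Optional:** stratify the other time-to-event analyses in 13.6 for efficiency, pooling small strata for rare outcomes. This corrects no error.

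The cost is wording only: no added patients, visits, data or time.
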